5.8.5.2 Guidelines for Diarrhea

Episodes of diarrhea have occurred in subjects receiving dabrafenib, trametinib, or both therapies in combination. Other, frequent causes for diarrhea including concomitant medications (e.g., stool softeners, laxatives, antacids, etc.), infections by *C. difficile* or other pathogens, partial bowel obstruction, etc., should be clinically excluded.

Guidelines regarding management and dose reduction for diarrhea considered to be related to study treatment by the investigator are provided in [Table 13](#).

Table 13 Management and Dose Modification Guidelines for Diarrhea

CTCAE Grade	Adverse Event Management	Action and Dose Modification
Uncomplicated Diarrhea ^a Grade 1 or 2	
 • Diet: stop all lactose containing products; eat small meals, BRAT-diet (banana, rice, apples, toast) recommended • Hydration: 8-10 large glasses of clear liquids per day (e.g., Gatorade or broth) • Loperamide: initially 4 mg, followed by 2 mg every four hours or after every unformed stool; maximum 16 mg/day. Continue until diarrhea free for 12 hours • Diarrhea ≥ 24h: loperamide 2 mg every two hours; maximum 16 mg/day. Consider adding oral antibiotics • Diarrhea ≥ 48h: loperamide 2 mg every two hours; maximum 16 mg/day. Add budesonide or other second-line therapies (otretotide, or tincture of opium) and oral antibiotics 	
 • Continue study treatment • If diarrhea is grade 2 for ≥ 48h, interrupt study treatment until diarrhea resolves to grade ≤1 • Restart study treatment at the same dose level
Uncomplicated Diarrhea ^a Grade 3 or 4 Any Complicated Diarrhea ^b	
 • Clinical evaluation mandatory • Loperamide: initially 4 mg, followed by 2 mg every four hours or after every unformed stool; maximum 16 mg/day. Continue until diarrhea free for 12 hours • Oral antibiotics and second-line therapies if clinically indicated • Hydration: intravenous fluids if clinically indicated • Antibiotics (oral or intravenous) if clinically indicated • Intervention should be continued until the subject is diarrhea free for ≥ 24 hours • Intervention may require hospitalization for subjects at risk of life-threatening complications 	
 • Interrupt study treatment until diarrhea resolves to grade ≤1 • Restart with study treatment reduced by one dose level^d • If 3 dose reductions of study treatment are clinically indicated, permanently discontinue study treatment

Table 13 Management and Dose Modification Guidelines for Diarrhea (Continued)

CTCAE = Common Terminology Criteria for Adverse Events

- a. **Uncomplicated diarrhea** defined by the absence of symptoms such as, cramping, nausea/vomiting \geq grade 2, decreased performance status, pyrexia, sepsis, neutropenia grade \geq 3, frank bleeding, and/or dehydration requiring intravenous fluid substitution
- b. **Complicated diarrhea** defined by the presence of symptoms such as, cramping, nausea/vomiting \geq grade 2, decreased performance status, pyrexia, sepsis, neutropenia grade \geq 3, frank bleeding, and/or dehydration requiring intravenous fluid substitution
- c. Loperamide should be made available prior to start of study treatment so loperamide administration can begin at the first signs of diarrhea
- d. Escalation of study treatment to previous dose level is allowed after consultation with the Novartis Medical Lead and in the absence of another episode of complicated or severe diarrhea in the 4 weeks subsequent to dose reduction

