Pyrexia ^a	
All Events:
 
 • Clinical evaluation for infection and hypersensitivity^c • Laboratory work-up^c • Hydration as required^d 
1st Event:^b
 
 • Administer anti-pyretic treatment as clinically indicated and initiate prophylactic treatment if associated with rigors, renal failure, dehydration or hypotension^e 
2nd Event^f
 
 • Within 3 days of onset of pyrexia 
 ○ Optimize anti-pyretic therapy ○ Consider oral corticosteroids (i.e., prednisone 10 mg) for at least 5 days or as clinically indicated^f 
Subsequent Events:
 
 • Within 3 days of onset of pyrexia: 
 ○ Optimize oral corticosteroid dose as clinically indicated for recalcitrant pyrexia^f ○ If corticosteroids have been tapered and pyrexia recurs, restart steroids ○ If corticosteroids cannot be tapered consult Novartis Medical Lead 	
1st Event:
 
 • Interrupt dabrafenib • Continue trametinib • Once pyrexia resolves to baseline, restart dabrafenib at the same dose level 
 ○ If fever was associated with rigors, renal failure, dehydration or hypotension, reduce dabrafenib by one dose level^g 
2nd Event:
 
 • Interrupt dabrafenib • Continue trametinib • Once pyrexia resolves to baseline, restart dabrafenib at the same dose level 
 ○ If fever was associated with rigors, renal failure, dehydration or hypotension, reduce dabrafenib by one dose level^g 
Subsequent Events:
 
 • Interrupt dabrafenib • Continue trametinib • Once pyrexia resolves to baseline, restart dabrafenib reduced by one dose level^g • If dabrafenib must be reduced to <75 mg BID, permanently discontinue dabrafenib. Trametinib may be continued

Table 12 Management and Dose Modification Guidelines for Pyrexia (Continued)

- a. Pyrexia is defined as a body temperature equal to or above 38.5 Celsius or 101.3° Fahrenheit.
- b. For subjects experiencing pyrexia, a clinical evaluation and laboratory work-up is mandatory for each event; anti-pyretic treatment should be started immediately at the first occurrence and prophylactic anti-pyretic treatment is recommended

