- c. Thorough clinical examination for signs and symptoms of infection or hypersensitivity is required; laboratory work-up should include full-blood-count, electrolytes, creatinine, blood urea nitrogen (BUN), C-reactive protein (CRP), liver-function tests, blood culture, and urine culture.
- d. Oral hydration should be encouraged in subjects without evidence of dehydration. Intravenous hydration is recommended in subjects experiencing pyrexia complicated by dehydration/hypotension.
- e. Anti-pyretic treatment may include acetaminophen, ibuprofen, or suitable anti-pyretic medication according to institutional standards. Prophylactic anti-pyretic treatment may be discontinued after three days in the absence of pyrexia
- f. In subject experiencing pyrexia complicated by rigors, severe chills, etc., which cannot be controlled with anti-pyretic medication, oral corticosteroids should be started at the 2nd event and doses should be gradually increased for subsequent events.
- g. Dabrafenib should be reduced by one dose level after three episodes of pyrexia complicated by rigors, severe chills, etc., which cannot be managed by best supportive care and increasing doses of oral steroids. Escalation of dabrafenib is allowed if no episode of pyrexia is observed in the 4 weeks subsequent to dose reduction.

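### Table 13's hold for complicated diarrhoea ends on diarrhoea grade ≤1 alone, so for Grade 1 complicated diarrhoea the interruption is over as soon as it starts

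*Protocol*

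**What the plan says.** Protocol Section 5.8.5.2, Table 13, covers diarrhoea that the investigator considers related to study treatment and has two rows.

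- **Row 1: uncomplicated Grade 1 or 2.** Treatment continues. If Grade 2 lasts 48 hours or more, the site is to "interrupt study treatment until diarrhea resolves to grade ≤1" and then restart at the same dose level.
- **Row 2: uncomplicated Grade 3 or 4, and complicated diarrhoea of any grade.** The site is to "Interrupt study treatment until diarrhea resolves to grade ≤1", and then "Restart with study treatment reduced by one dose level". The management column makes clinical evaluation mandatory and mentions possible hospitalisation.

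Footnote b defines complicated diarrhoea by the presence of features such as cramping, nausea or vomiting of Grade 2 or more, "decreased performance status, pyrexia, sepsis, neutropenia grade" 3 or more, frank bleeding, and dehydration needing intravenous fluids. It sets no minimum grade for the diarrhoea itself. Footnote d allows re-escalation after consultation with the Medical Lead, "in the absence of another episode of complicated or severe diarrhea in the 4 weeks subsequent to dose reduction".

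**The concern.** Row 2 treats complicated diarrhoea as the equal of uncomplicated Grade 3 or 4 and orders a hold. The reason for the hold at low grade is the complication, since uncomplicated Grade 1 diarrhoea in row 1 calls for no hold at all. Yet the release depends only on the diarrhoea grade. A subject who enters row 2 with Grade 1 diarrhoea meets the release condition before any dose is withheld, and may resume at once, one level lower, with the complication still active. A safety rule that reads as a hold therefore works as a dose reduction only. At stake is whether sites withhold drug during the complication as the row appears to intend. No efficacy estimate is involved.

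**Working it through.** There is no planned figure to reproduce. The check is one of logic, in three steps.

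**Step 1. Apply the release test to each grade that can enter row 2.**

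| Diarrhoea at entry | Diarrhoea grade ≤1 already? | Hold under row 2 |
|---|---|---|
| Complicated, Grade 1 | Yes, at onset | None; dose reduction only |
| Complicated, Grade 2 | No | Until Grade 1 |
| Complicated or uncomplicated, Grade 3 or 4 | No | Until Grade 1 |

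Only the Grade 1 line fails.

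**Step 2. Compare with the other rules in Section 5.8 that release a hold at grade 1 or below.**

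| Table | Rows | Lowest entry point |
|---|---|---|
| 5, general | 3 (Grades 2, 3, 4) | Grade 2 |
| 8, QTc | 1 | QTc of 501 msec or more |
| 10, rash | 2 (Grades 2, ≥3) | Grade 2 |
| 11, hand-foot skin reaction | 2 (Grades 2, ≥3) | Grade 2 |
| 13, row 1 | 1 | Grade 2 |
| 13, row 2 | 1 | **Grade 1, if complicated** |
| 16, RPED | 1 (Grade 2-3) | Grade 2 |
| 17, pneumonitis | 2 (Grades 2, 3) | Grade 2 |

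Total: 3 + 1 + 2 + 2 + 1 + 1 + 1 + 2 = 13. Table 17 also allows a restart after Grade 4 pneumonitis that recovers to grade 1 or below, with approval. Counting that as a release rule makes 14, and its entry point is Grade 4. On either count, Table 13 row 2 is the only rule whose release condition can be true at entry. Row 1 of the same table uses the same release condition after a Grade 2 trigger, where it works.

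**Step 3. Look for other text that would give the Grade 1 hold some length.**

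- Table 13, management column: the requirement to be free of diarrhoea for 24 hours sets how long the supportive intervention continues. It does not govern the drug hold.
- Table 13, footnote d: this governs return to the earlier dose level, not the end of the hold.
- Table 12 (Section 5.8.5.1): for related fever, defined as 38.5 °C or more, dabrafenib is interrupted until the fever is back to baseline. Its instruction for trametinib is "Continue trametinib".
- Table 5 (Section 5.8.2): this applies to related events without their own guideline. It holds study treatment at Grades 3 and 4. At Grade 2 the hold is left to clinical judgement.

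For Grade 1 diarrhoea the position is therefore:

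- **With related fever:** dabrafenib is held by Table 12. Trametinib has no effective hold, although row 2 lowers its dose.
- **With a related Grade 3 or 4 complication that has no specific guideline, such as neutropenia:** Table 5 holds study treatment.
- **With a lower-grade complication such as Grade 2 vomiting:** no firm hold applies. Row 2's reduction and evaluation still do.

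**The case against.** The strongest reply is that little is lost in practice. Section 5.8 is worded as guidance, row 2 makes clinical evaluation mandatory, and an investigator facing diarrhoea with sepsis or bleeding will not resume dosing because the stool count is low. Tables 12 and 5 cover fever and the severe related complications. All of this stands, and it is why the point is minor. It does not repair the row, because the protection comes from other tables or from judgement and not from the hold that row 2 states.

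A second reply is that reduction alone may be what was meant at Grade 1. The text does not say so. The row gives one instruction for everything in it, beginning with an interruption, and that instruction is meaningless for one of its entry routes.

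A reader might go further and infer that Tables 12 and 13 contradict each other when diarrhoea comes with fever, since Table 12 keeps trametinib going while Table 13 interrupts and reduces study treatment. The documents do not support that. "Continue trametinib" in Table 12 states what to do about the fever; it does not forbid holding or reducing trametinib for another toxicity. Table 14 shows how the tables can combine: its first row keeps study treatment at the same dose for a small creatinine rise and also sends any fever to the pyrexia guideline, which interrupts dabrafenib. An instruction to continue in one table can thus sit beside a hold from another. What remains is that Table 13 lacks the cross-reference to the pyrexia guideline that Table 14 has.

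**Conclusion.** The point holds, at minor severity. For Grade 1 complicated diarrhoea, the interruption in Table 13 row 2 is satisfied at onset, leaving only a one-level reduction and mandatory evaluation regardless of whether the complication has settled. It is the only release rule of its kind in Section 5.8 with this defect.

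This rests on three readings:

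- The diarrhoea is judged related to study treatment, as Table 13 requires.
- The release line is taken literally.
- Study treatment in row 2 means both drugs. Section 5 lets the term mean either drug alone or the combination, but Table 3 marks both drugs for diarrhoea.

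The documents do not say how often Grade 1 complicated diarrhoea occurs, so no number of affected subjects can be given. A reader might also infer an effect on the response rate or the sample size; nothing in the protocol or SAP supports one. Any trace would lie in the summaries of dose reductions and interruptions by drug (SAP Section 2.4.1.4), and its size is unknown.

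**What to change.** Keep the row 2 release line, "Interrupt study treatment until diarrhea resolves to grade ≤1", and add after it: *and the complicating signs or symptoms have resolved to baseline*.

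The added condition should be baseline, not grade ≤1 or baseline. With the looser wording, a Grade 1 complication such as mild cramping would again meet the test at onset. Baseline also matches Table 12's release for fever. For uncomplicated Grade 3 or 4 diarrhoea the added clause has nothing to act on, so that part of the row is unchanged.

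The cost is a slightly longer hold in some subjects, mainly where a feature such as performance status is slow to recover. Section 5.8.1 already requires Medical Lead approval to restart after 21 days or more of interruption, which covers long holds. The edit is one line in one table. SAP Section 2.1.1 gives last patient last visit as 19-Apr-2021, so nothing is asked of this study; the change is for a later protocol that reuses Table 13.

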5.8.5.3 Guidelines for Renal Insufficiency

Cases of renal insufficiency have occurred in subjects receiving dabrafenib and the combination of dabrafenib and trametinib. Prior to start of study treatment, concomitant medications should be reviewed for the potential risk of inducing nephrotoxicity and concomitant medications should be modified if clinically possible.

Guidelines regarding management and dose reduction for renal insufficiency considered to be related to study treatment by the investigator are provided in [Table 14](#).

Table 14 Management and Dose Modification Guidelines for Renal Insufficiency

Serum Creatinine Level	Adverse Event Management	Action and Dose Modification
Serum creatinine increase >0.2 mg/dL (18 umol/L) but ≤0.5 mg/dL (44 umol/L) above baseline	
 Recheck serum creatinine within 1 week Serum creatinine increase > 1 week: contact Novartis Medical Lead If pyrexia is present, treat pyrexia as per guidelines^a 	
 Continue study treatment at the same dose level
Serum creatinine increase >0.5 mg/dL (44 umol/L) above baseline or serum creatinine >2 mg/dL (> 177 umol/L)	
 Monitor serum creatinine ≥ 2-times per week Hospitalization may be necessary if serum creatinine cannot be monitored frequently If pyrexia is present, treat pyrexia per guidelines^a Consult nephrologist if clinically indicated Perform renal biopsy if clinically indicated, for example: 
 Renal insufficiency persists despite volume repletion Subject has new rash or signs of hypersensitivity (such as elevated eosinophil count) 	
 Interrupt study treatment until serum creatinine recovers to baseline Restart with study treatment^b

NSAIDs = non-steroidal anti-inflammatory drugs

- NSAIDs can induce renal insufficiency, especially in subjects with dehydration; encourage oral fluids or consider intravenous fluids as clinically indicated. See guidelines for pyrexia Section 5.8.5.1.
- Investigator may restart at either the same or a reduced dose level. Escalation of study treatment to previous dose level is allowed if another episode of renal insufficiency does not occur after 4 weeks of dose reduction. Consultation with Novartis Medical Lead is required before restarting study treatment if there is evidence of thrombotic microangiopathy.

5.8.5.4 Guidelines for Visual Changes or Specified Ophthalmic Examination Findings

Episodes of visual changes have been observed in subjects receiving trametinib, dabrafenib, and combination therapy. An ophthalmologist should be consulted if changes in vision develop. However, if the visual changes are clearly unrelated to study treatment (e.g., allergic conjunctivitis), then monitor closely as it may be reasonable to defer ophthalmic examination.

Treatment with dabrafenib has been associated with the development of uveitis, including iritis. Monitor patients for visual signs and symptoms (such as, change in vision, photophobia and eye pain) during therapy. Special attention should be given to retinal findings (e.g., retinal pigment epithelial detachment (RPED) or retinovascular abnormalities (i.e., branch or central retinal vein occlusions (RVO)). For events of visual changes (regardless of severity) for which an ophthalmic examination is conducted, a blood sample for PK analysis must be drawn as close as possible to the time of the event.

Guidelines regarding management and dose reduction for visual changes and/or ophthalmic examination findings considered to be related to study treatment are provided in [Table 15](#).

Table 15 Management and Dose Modification Guidelines for Visual Changes and/or Ophthalmic Examination Findings

CTCAE Grade ^a	Adverse Event Management	Action and Dose Modification
Grade 1 ^b	
 Consult ophthalmologist within 7 days of onset 	
 If dilated fundus examination cannot be performed within 7 days of onset, interrupt trametinib until RPED and RVO can be excluded by retina specialist/ophthalmologist. If subject is receiving trametinib/dabrafenib combination therapy dabrafenib may be continued. If RPED and RVO excluded, continue (or restart) trametinib at same dose level If RPED suspected or diagnosed: see RPED dose modification Table 16 below; report as SAE if diagnosed. If RVO: Permanently discontinue study treatment
Grade 2 and Grade 3	
 Consult ophthalmologist immediately Interrupt trametinib. If subject is receiving trametinib/dabrafenib combination therapy dabrafenib may be continued. 	
 If RPED and RVO excluded, restart trametinib at same dose level. If RPED diagnosed, see RPED dose modification table below; report as SAE. If RVO: Permanently discontinue trametinib and report as SAE.
Grade 4	
 Consult ophthalmologist immediately Interrupt trametinib. If subject is receiving trametinib/dabrafenib combination therapy dabrafenib may be continued. 	
 If RPED and RVO excluded, may consider restarting trametinib at same or reduced dose after discussion with study Medical Lead If RVO or RPED diagnosed, permanently discontinue trametinib and report as SAE.

Abbreviations: RPED = retinal pigment epithelial detachment; CTCAE = Common Terminology Criteria for Adverse Events;

RVO = retinal vein occlusion; SAE = serious adverse event

- a. Refers to CTCAE Version 4.0 'Eye disorders – Other, specify'
- b. If visual changes are clearly unrelated to study treatment (e.g., allergic conjunctivitis), monitor closely but ophthalmic examination is not required.

Table 16 Recommended dose modifications for trametinib for retinal pigment epithelial detachments (RPED)^a

CTCAE Grade	Action and Dose Modification
Grade 1 RPED (Asymptomatic; clinical or diagnostic observations only)	
 • Continue treatment with retinal evaluation monthly until resolution. If RPED worsens follow instructions below
Grade 2-3 RPED (Symptomatic with mild to moderate decrease in visual acuity; limiting instrumental ADL)	
 • Interrupt trametinib • Retinal evaluation monthly • If improved to ≤ Grade 1, restart trametinib at lower dose (reduced by 0.5 mg) or discontinue in patients taking trametinib 1 mg daily

- a. Refers to CTCAE Version 4.0 'Retinopathy'

Ophthalmologic Exam

At certain time points in the trial (see [Table 20](#)) and if visual changes develop (as described in this section below), an eye exam is indicated. The exam will include best corrected visual acuity, tonometry, slit lamp biomicroscopic examination, visual field examination, and dilated indirect funduscopy with special attention to retinal abnormalities. Optical coherence tomography is strongly recommended at scheduled visits, and if retinal abnormalities are suspected. Other types of ancillary testing including color fundus photography and fluorescein angiography are also recommended if clinically indicated.

For adverse events of uveitis, no dose modifications are required as long as effective local therapies can control ocular inflammation. If uveitis does not respond to local ocular therapy, interrupt dabrafenib and hold until resolution of ocular inflammation. Then restart dabrafenib reduced by one dose level.

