4.2.3 Subject Completion Criteria

A subject will be considered to have completed the study if the subject dies during the study treatment or follow-up period. The cause of death will be documented in the eCRF. A subject will be considered to have withdrawn from the study if the subject has not died and is lost to

follow-up or has withdrawn consent, or if the study is completed. The definition of study completion was described in protocol Section 3.1.

5 Study treatments

The term ‘study treatment’ is used throughout the protocol to describe any combination of products received by the subject as per the protocol design. Study treatment may therefore refer to the individual study treatments or the combination of those study treatments.

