5.8 Dose Modification Guidelines

The severity of adverse events will be graded utilizing the CTCAE v4.0. Guidelines for dose modifications and interruptions for management of common toxicities associated with the study treatment are provided in this section.

Dose modifications in response to adverse events are permitted. Dose modification guidelines include:

- general guidelines for clinically significant toxicities related to study treatments and
- specific guidelines for adverse events of special interest, which are events that have been observed with higher frequency or severity in subjects receiving dabrafenib, trametinib, or a combination of both therapies.

With the exceptions of pyrexia (likely related to dabrafenib) and LVEF (likely related to trametinib), the guidance suggests that both therapies be reduced simultaneously in response to toxicities that are considered by the investigator to be treatment related.

Table 3 Categories of Dose Modification Guidelines

Adverse Event	Dabrafenib	Trametinib	Section
General Guidelines for Clinically Significant Toxicities	X	X	5.8.2
Guidelines for Specific Adverse Events			
Cardiovascular Adverse Events			
LVEF		X	5.8.3.1
Hypertension	X	X	5.8.3.2
Prolonged QTc	X	X	5.8.3.3
Skin –Related Adverse Events (Except cuSCC) ^a			
Rash	X	X	5.8.4.1
Hand-Foot Skin Reaction	X	X	5.8.4.2
Other Adverse Events			
Pyrexia	X		5.8.5.1
Diarrhea	X	X	5.8.5.2
Renal Insufficiency	X	X	5.8.5.3
Visual Changes	X	X	5.8.5.4
Pneumonitis	X	X	5.8.5.5
Liver Chemistry Stopping Criteria	X	X	5.9.1

a. Refer to Section [5.8.4.4](#) for management of cuSCC

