5.8.3.1 Left Ventricular Ejection Fraction (LVEF)

Decreases of the left-ventricular-ejection-fraction (LVEF) have been observed in subjects receiving trametinib monotherapy and in combination with dabrafenib. Therefore, ECHOs must be performed to assess cardiac ejection fraction in regular intervals as outlined in the Time and Events Table ([Table 20](#)). All ECHOs will be collected; instructions are provided in

the Study Procedures Manual (SPM). Dose modification guidance and stopping criteria for LVEF decrease are provided in [Table 6](#).

Table 6 Dose Modification Guidelines and Stopping Criteria for LVEF Decrease

Clinic	LVEF-drop (%) or CTCAE grade	Action and Dose Modification
Asymptomatic	Absolute decrease of >10% in LVEF compared to baseline and ejection fraction below the institution's low LLN	
 • Interrupt trametinib and repeat ECHO within 2 weeks^{a,b} • If the LVEF recovers within 4 weeks (defined as LVEF ≥LLN and absolute decrease ≤10% compared to baseline) 
 ○ Consult with the Novartis Medical Lead and request approval for restart ○ If approve, restart treatment with trametinib reduced by one dose level ○ Repeat ECHO at 2, 4, 8 and 12 weeks after re-start; continue in intervals of 12 weeks thereafter • If repeat LVEF does not recover within 4 weeks 
 ○ Consult with cardiologist ○ Permanently discontinue trametinib ○ Report as SAE ○ Repeat ECHO after 2, 4, 8, 12, and 16 weeks or until resolution
Symptomatic ^c	Grade 3: resting LVEF 39-20% or >20% absolute reduction from baseline	
 • Permanently discontinue trametinib^b • Interrupt dabrafenib.^d • Report as SAE • Consult with cardiologist • Repeat ECHO after 2, 4, 8, 12, and 16 weeks or until resolution^{b,d}
	Grade 4: resting LVEF <20%	

Abbreviations: CTCAE = Common Terminology Criteria for Adverse Events; ECHO = echocardiogram; LLN = lower limit of normal; LVEF = left ventricular ejection fraction;

- a. If ECHO does not show LVEF recovery after 2 weeks, repeat ECHO 2 weeks later.
- b. If recurrent episodes of LVEF reduction occur in subjects receiving dabrafenib monotherapy, consult Novartis Medical Lead.
- c. Symptoms may include: dyspnea, orthopnea, and other signs and symptoms of pulmonary congestion and edema.

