5.8.5.5 Guidelines for Pneumonitis

Pneumonitis has been observed in subjects receiving trametinib. To reduce the risk of pneumonitis, subjects will be monitored closely for symptoms, evaluated with imaging and functional tests. Dose modification and supportive care guidelines for pneumonitis are described in [Table 17](#).

Table 17 Management and Dose Modification Guidelines for Pneumonitis

CTCAE Grade	Adverse Event Management	Action and Dose Modification
Grade 1	
 • CT scan (high-resolution with lung windows) recommended • Clinical evaluation and laboratory work-up for infection • Monitoring of oxygenation via pulse-oximetry recommended • Consultation of pulmonologist recommended 	
 • Continue trametinib at current dose
Grade 2	
 • CT scan (high-resolution with lung windows) • Clinical evaluation and laboratory work-up for infection • Consult pulmonologist • Pulmonary function tests –if < normal, repeat every 8 weeks until ≥ normal • Bronchoscopy with biopsy and/or BAL recommended • Symptomatic therapy including corticosteroids if clinically indicated 	
 • Interrupt trametinib until recovery to grade ≤1 • Restart with trametinib reduced by one dose level • Escalation to previous dose level after 4 weeks and consultation with Novartis Medical Lead possible • If no recovery to grade ≤1 within 4 weeks, permanently discontinue study treatment
Grade 3	
 • CT scan (high-resolution with lung windows) • Clinical evaluation and laboratory work-up for infection • Consult pulmonologist • Pulmonary function tests-if < normal, repeat every 8 weeks until ≥ normal • Bronchoscopy with biopsy and/or BAL if possible • Symptomatic therapy including corticosteroids as clinically indicated 	
 • Interrupt trametinib until recovery to grade ≤1 • After consultation with Novartis Medical Lead, study treatment may be restarted reduced by one dose level • If no recovery to grade ≤1 within 4 weeks, permanently discontinue study treatment
Grade 4	
 • Same as grade 3 	
 • Permanently discontinue study treatment or if recovers to grade ≤1 obtain Novartis Medical Lead approval if patients is expected to benefit from the study treatment

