2.1.3 General definitions

2.1.3.1 Study drug and study treatment

Study drug and study treatment both refer to Dabrafenib in Combination with Trametinib.

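### Table 15 (retinal vein occlusion) and Table 17 (pneumonitis) switch between trametinib and an ambiguous study treatment, so the protocol contradicts itself on whether dabrafenib also stops

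*Protocol*

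**What the plan says.** **RVO.** Protocol Section 5.8.5.4, Table 15, sets the action by grade. If RVO is found, the Grade 1 row says "Permanently discontinue study treatment". The Grade 2 and 3 row says "Permanently discontinue trametinib and report as SAE". The Grade 4 row says "If RVO or RPED diagnosed, permanently discontinue trametinib and report as SAE". In all three rows the interim hold is on trametinib, with dabrafenib allowed to go on.

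**Pneumonitis.** In Protocol Section 5.8.5.5, Table 17, the first dose action at Grades 2 and 3 is "Interrupt trametinib until recovery to grade" 1 or lower. The Grade 2 restart line names trametinib; the Grade 3 restart line names study treatment. At both grades, no recovery within 4 weeks leads to a permanent stop of study treatment.

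**Definitions.** The opening of Protocol Section 5 says: "Study treatment may therefore refer to the individual study treatments or the combination of those study treatments". SAP Section 2.1.3.1 says: "Study drug and study treatment both refer to Dabrafenib in Combination with Trametinib".

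**Overview text.** Section 5.8 says that, pyrexia and LVEF apart, "the guidance suggests that both therapies be reduced simultaneously in response to toxicities" that the investigator considers treatment related. Table 3 marks both drugs for visual changes and pneumonitis, and trametinib only for LVEF. For a symptomatic LVEF decrease, Table 6 adds "Interrupt dabrafenib".

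**The concern.** A permanent stop either withdraws dabrafenib from a patient who may be benefiting or, if it is read too narrowly, keeps a patient on a drug that the protocol may have meant to withdraw. An instruction of that weight should not depend on how a site reads one term. RVO is also a protocol-specific SAE in Section 7.3.2.2.

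The choice also reaches the analysis:

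- Exposure, dose intensity and dose modifications are reported by drug (SAP Sections 2.4.1.1 to 2.4.1.4).
- Discontinuation of the treatment phase is derived from the discontinuation pages of both drugs (SAP Section 2.3.1).
- The AE overview counts AEs leading to permanent discontinuation of study treatment (SAP Section 2.8.1), a term that the SAP equates with the combination.
- The on-treatment AE period runs to 30 days after the last dose of either drug (SAP Section 2.1.3.6), so it lengthens if dabrafenib continues.

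**Working it through.** No arithmetic applies. The check sets the rows side by side and then tests each permitted meaning of the term.

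| Event and grade | Hold | Restart | Permanent stop |
|---|---|---|---|
| RVO, Grade 1 (Table 15) | trametinib, if the eye examination is delayed | not applicable | study treatment |
| RVO, Grades 2-3 | trametinib | not applicable | trametinib |
| RVO, Grade 4 | trametinib | not applicable | trametinib |
| Pneumonitis, Grade 2 (Table 17) | trametinib | trametinib, one level lower | study treatment, if no recovery |
| Pneumonitis, Grade 3 | trametinib | study treatment, one level lower | study treatment, if no recovery |

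**If study treatment means the combination** (the SAP's definition, and one of the two meanings in Protocol Section 5): RVO stops two drugs at Grade 1 and one drug at Grades 2 to 4. For Grade 3 pneumonitis, dabrafenib, which was never held, would be restarted at a lower dose.

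**If study treatment means trametinib alone** (the other meaning in Protocol Section 5): the three RVO rows agree, and the Grade 3 pneumonitis restart makes sense. Dabrafenib then continues even when pneumonitis has not recovered. However, the Grade 1 cell of Table 15 names trametinib and dabrafenib individually in its other lines, so a reader would normally take the change of term as deliberate. This reading also departs from the SAP.

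Neither meaning is excluded. Two sites could therefore act differently on the same Grade 1 RVO, or on the same unrecovered pneumonitis, and both be within the protocol.

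**Lesser mismatches between overview and detail:**

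- Section 5.8 suggests reducing both drugs together and does not list visual changes or pneumonitis as exceptions. Table 15 (the Grade 4 option), Table 16 and Table 17 (Grade 2) reduce trametinib alone.
- Table 3 marks LVEF as trametinib only, whereas Table 6 also interrupts dabrafenib when the decrease is symptomatic.

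**The case against.** The strongest reply is that the protocol moves from general to specific. Section 5.8 separates general from event-specific guidance, Section 5.8.2 limits Table 5 to events without their own guidelines, and Table 3 works as an index. Sections 4.2.1 and 5.2 also allow one drug to continue when the other stops. This disposes of much of what a reader might infer, in particular that four event types carry contradictory orders:

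- **LVEF:** Table 6 names the drug for each dose action, so a site following it has no choice to make. The defect is a missing mark in Table 3.
- **Visual changes:** Section 5.8.5.4 also contains the uveitis rule, which holds and reduces dabrafenib. That explains the dabrafenib mark in Table 3.
- **The both-drugs sentence in Section 5.8:** it is a suggestion about reductions. It is not a rule for holds or permanent stops.
- **Pneumonitis against Table 3:** three of the four grade rows of Table 17 contain a study treatment action, so the two marks in Table 3 can be consistent with it. The Grade 2 non-recovery line can be read as a step up from holding one drug to stopping both.

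The reply does not reach the core. The RVO conflict and the Grade 3 pneumonitis restart lie inside the specific tables, so giving those tables precedence cannot resolve them. Permission to continue one drug does not say what study treatment means in a given row.

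The objection that the SAP reports by drug also stands in part: the data will show which drug was stopped. They will not show whether that followed the protocol.

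**Conclusion.** The point holds as an internal inconsistency. Table 15 gives two different permanent-stop instructions for RVO across its three grade rows if study treatment means the combination. Table 17 has three lines at Grades 2 and 3 that use the same term after a hold on trametinib alone. The lesser mismatches are matters of tidying.

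The effect on patients or results cannot be quantified, because the documents give no counts of RVO or pneumonitis. Three stronger inferences are not supported:

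- That sites did treat patients differently. The written RVO difference is by grade. Variation between sites is possible through the two meanings of the term, but it is not shown.
- That all these events are protocol-specific SAEs. Section 7.3.2.2 lists RVO but not pneumonitis.
- That the primary result is compromised. The exact interval for the objective response rate in all treated subjects is calculated in the same way whichever drug is stopped.

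The conclusion rests on the current text alone, not on the amendment history, and takes no position on which instruction is clinically right.

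**What to change.** The sponsor should reconcile the RVO rows of Table 15 and the study treatment lines of Table 17 so that each names the drug or drugs affected. Section 5.8 and Table 3 should be brought into agreement with the event tables, with a sentence stating that the event-specific tables, once reconciled, govern. The choice of drug in each row is for the sponsor's clinical team.

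The cost is clarification or amendment text only. SAP Section 2.1.1 gives the last patient's last visit as 19-Apr-2021, so the change cannot alter dosing already given in this trial. What it can still do is correct the text and support reporting: for any RVO or pneumonitis event, the study report should list the action taken for dabrafenib and for trametinib separately. It should also state whether the count of AEs leading to discontinuation of study treatment includes subjects who stopped only one drug. The SAP already collects dose actions by drug, so this needs no new data.
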